- *Vibrio cholerae*
- *Yersinia enterocolitica*
- *Cryptosporidium*
- *Cyclospora cayetanensis*
- *Entamoeba histolytica*
- *Giardia lamblia*

*Shiga-like toxin-producing *E. coli* (STEC) genes (stx1 and stx2) are differentiated by QIAstat-Dx Gastrointestinal Panel 2

Follow-up

Primary outcome and most secondary outcomes will be assessed using medical record review. For selected secondary outcomes, we will follow the patients with electronic survey sent via e-mail two weeks after the study visit. The survey is established, and the answers are retained on the Red-CAP -platform. With the survey we estimate recovery of the child (duration of symptoms, return to day care or school). If the symptoms have not resolved by two weeks, an automated follow-up questionnaire will follow four weeks after the study visit.

Sample size calculation

With a composite primary outcome consisting of 1) use of correctly targeted antibiotic treatment, 2) avoiding incorrect antibiotic treatment and 3) identification of conditions in need for a precise follow-up, we regard a clinically significant difference if the proportion of children with a positive composite outcome is 20 % in the intervention group and 10 % in the control group. With an α error of 5% and a statistical power of 80 % and using 1:1 randomization, with an assumption of 20 % loss in retaining requested fecal samples, we need 263 children in intervention group and 263 controls, for a total of 526 children. We use all children with alternative sample types (rectal swab or vomit) for the diagnostic analysis.

Primary outcome

To assess the test's impact on clinical decision making, primary outcome composite includes three questions:

- 1) Was correctly targeted antimicrobial treatment started
- 2) Was untargeted antimicrobial treatment avoided
- 3) Was specific follow-up planned due to risk of complications (e.g. EHEC and hemolytic uremic syndrome)

within 72 hours from initial contact in Pediatric Emergency Room?

When any of these questions is answered YES, the composite variable is considered positive. Antimicrobial treatment is considered appropriate if a bacterial pathogen has been found and the patient meets criteria for severe gastroenteritis (aged under 1 year or immunocompromised or hospitalized due to gastroenteritis).

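### The any-YES primary composite counts every child spared an untargeted antimicrobial as positive, which does not fit the planned 10% and 20% rates behind the 263 per arm

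*Protocol*

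**What the plan says.** Protocol 3.1, Primary outcome, introduces the endpoint as assessing the test's "impact on clinical decision making, primary outcome composite includes three questions". The questions are whether correctly targeted antimicrobial treatment was started, "Was untargeted antimicrobial treatment avoided", and whether specific follow-up was planned because of a risk of complications. All are judged "within 72 hours from initial contact in Pediatric Emergency Room". The scoring rule is "When any of these questions is answered YES, the composite variable is considered positive". The only further definition is "Antimicrobial treatment is considered appropriate if a bacterial pathogen has been found and the patient meets criteria for severe gastroenteritis", with the severity criteria listed after it.

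Protocol 3.1, Sample size calculation, names the second component as "avoiding incorrect antibiotic treatment" and plans on a "proportion of children with a positive composite outcome is 20 % in the intervention group and 10 % in the control group". With a 5% α error, 80% power, 1:1 allocation and "with an assumption of 20 % loss in retaining requested fecal samples", it arrives at 263 per arm, 526 in total.

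Three other places bear on the point. Section 3.1 enrols children under 16 with acute gastrointestinal symptoms and does not confine entry to candidates for antibiotics. Section 1 says that most such children need nothing beyond rehydration. Section 3.1, Sample Collection and Pathogen Detection, holds back control-arm results until 72 hours.

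**The concern.** The scoring rule and the planning rates are both fixed in the protocol, and they do not describe the same variable. A child who receives no antimicrobial at all has, in plain language, avoided an untargeted one. Question 2 is then YES and the composite is positive. In a population where most children need only rehydration, one would expect a high positive rate, not 10% or 20%.

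Two things are at stake. First, the sample size and power statement rest on rates that the written rule does not produce, so the power for the sole primary endpoint is unknown. Second, under the literal rule questions 1 and 3 alter a child's score only if that child also received an untargeted antimicrobial. The composite would mostly measure untargeted use. Targeted treatment and follow-up, two of the three benefits hypothesised in section 2, would hardly affect it and would be seen mainly through the secondary outcomes.

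**Working it through.** **Inputs from Protocol 3.1:** 10% vs 20% positive, α 5% (taken as two-sided; the text does not say), power 80%, 1:1 allocation, 20% loss, 263 per arm.

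**1. Reproduce the stated size.** Two-proportion formula with pooled variance under the null, p̄ = 0.15:

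n = [1.96·√(2·0.15·0.85) + 0.8416·√(0.10·0.90 + 0.20·0.80)]² / 0.10² = (0.990 + 0.421)² / 0.01 ≈ 199 per arm.

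Continuity correction: (199/4)·[1 + √(1 + 4/(199·0.10))]² = 218.5, so 219. Then 219 × 1.2 = 262.8, so 263. The stated number follows from 10% vs 20%. After the assumed loss, 263 × 0.8 ≈ 210 per arm are evaluable.

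**2. What the rule implies.** A child is negative only if an untargeted antimicrobial was given and questions 1 and 3 are both NO. With u the share of an arm given an untargeted antimicrobial:

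P(positive) ≥ 1 − u, hence u ≥ 1 − P(positive).

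- Control: u ≥ 1 − 0.10 = 90%.
- Intervention: u ≥ 1 − 0.20 = 80%.
- If u is below 50% in an arm, more than 50% of that arm is positive.

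This step is logic and needs no outside figure.

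**3. Power under the literal rule.** The protocol gives no u, so a range is assumed. As an illustration, let the panel halve u and let questions 1 and 3 add nothing. The rates are then 1 − u vs 1 − u/2, with difference d = u/2. Corrected power replaces n by m = n·(1 − 1/(n·d))² in

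Φ{[d·√m − 1.96·√(2p̄(1−p̄))] / √(p₁(1−p₁) + p₂(1−p₂))}.

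Example, u = 10%, n = 210: rates 0.90 vs 0.95, d = 0.05, p̄ = 0.925, m = 210·(1 − 1/10.5)² = 171.9. Power = Φ[(0.656 − 0.730)/0.371] = 0.42.

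| Control u, halved | Positive, control vs intervention | Power at 210 (263) per arm, corrected | Power at 210 (263), uncorrected | Corrected n per arm for 80% | × 1.2 |
|---|---|---|---|---|---|
| 5% | 95% vs 97.5% | 19% (25%) | 27% (33%) | 984 | 1181 |
| 10% | 90% vs 95% | 42% (52%) | 49% (59%) | 474 | 569 |
| 20% | 80% vs 90% | 78% (87%) | 82% (90%) | 219 | 263 |
| 30% | 70% vs 85% | 95% (98%) | 96% (99%) | 134 | 161 |

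Reaching 80% power needs a control u of about 21% at 210 per arm (17% at 263) with the correction, or 19% (16%) without.

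**4. Where 263 would fit.** 80% vs 90% mirrors 10% vs 20% and needs the same n. On these assumptions 263 suits the literal endpoint only near a control u of 20%, halved. The protocol states no such rates.

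**The case against.** The strongest reply is that the literal reading was never meant. The composite is framed as the test's effect on decisions, and the sample size text speaks of "avoiding incorrect antibiotic treatment". On that view avoided means averted: a treatment that would otherwise have been given was not. The very implausibility of 80–90% untargeted use suggests this intention, and 10% vs 20% could then be coherent. It is a fair reading, but the text does not define it. The protocol says when treatment counts as appropriate; it does not say which children question 2 applies to or how an averted treatment is recognised.

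A second reply is that delayed release in controls does not block scoring. Stool is analysed in both arms, so treatment actually given can be classified afterwards against the PCR result, and an admitted child may be retested the next day. This is right for treatments given. It does not settle how to judge one that was never given, when control clinicians generally lack the study result for the whole outcome window.

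A third reply is that underpowering is not shown: the power table rests on assumptions, and power may exceed 80%. That also stands. The section 1 remark on rehydration concerns need, not use, and supplies no value of u.

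Finally, scoring detail could sit in an analysis plan that is not at hand. But the any-YES rule and the planning rates are both set in the protocol, and the mismatch lies between those two.

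**Conclusion.** The concern holds. As worded, the composite has a positive rate of at least 1 − u in each arm, so 10% and 20% require untargeted antimicrobials in at least 90% and 80% of children, and the protocol gives no support for such use. The arithmetic from 10% vs 20% to 263 can be reproduced; the fault is that those rates do not belong to the endpoint as written. The bounds in step 2 rest only on the protocol's wording. The power figures rest on assumed u, a halving of u by the panel and no contribution from questions 1 and 3; they show that power could lie well below or above 80%, not that it is low. Under the averted reading the rates might stand, but the endpoint is then undefined at its central question. Either way the primary outcome and its power statement must be reconciled.

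**What to change.** Amend section 3.1 before any outcome is scored, in one of two ways.

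- **Keep any-YES and question 2 as worded.** State an assumed u for each arm, derive the expected positive rates (at least 1 − u), and restate the power at 263 enrolled, about 210 evaluable, per arm. This needs no new data, since record review is already planned. It leaves questions 1 and 3 with little influence, which should be acknowledged.
- **If avoided means averted, define it.** State in the primary outcome which children question 2 applies to and how it is judged in the same way in both arms, given that control results are held until 72 hours. Because clinicians see results at different times by arm, basing the judgement on information available before any result, with the assessor unaware of allocation where feasible, would help. Then confirm or restate 10% and 20% and the power. This adds one judgement to the record review.

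Any treatment or follow-up indication remains for the investigators to set. The cost is an amendment to the outcome wording, planning rates and power statement. The restated power may be less favourable than 80%, or the enrolment target may have to change.

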3. METHODS

3.1 Clinical significance of real time PCR panel for gastrointestinal pathogens (RCT)

Study design and oversight

This is an investigator-driven academic clinical trial with randomized controlled study setting conducted at the Pediatric Emergency Department of Oulu University Hospital. The samples are processed in the NordLab clinical microbiology laboratory at Oulu University Hospital, where the diagnostic device is already in clinical use. The device has been as acquired by NordLab under national procurement legislation.

Study population and inclusion criteria

For eligibility, children aged under 16 years arriving in pediatric emergency due to acute gastrointestinal symptoms (vomiting and/ or diarrhea and/or abdominal pain and/or watery stool) will be assessed. Pediatric nurses in the ED screen children for eligibility upon arrival. Exclusion criteria are the need for cardiopulmonary resuscitation, immediate transfer to the intensive care unit, haematological disease or other severe immunosuppression, bloody diarrhea or a clinical suspicion of typhoid/paratyphoid fever. Otherwise, patients with comorbidities or prior antibiotic treatment are included. The multiplex PCR test is used only in children admitted to the study or those that meet the exclusion criteria.

Randomization

Before initiation of the study, a biostatistician who is not involved in the data collection creates a randomization list using a computer-generated random sequence of numbers, randomization being performed in permuted blocks of sizes varying randomly between 4 and 6. After obtaining written informed consent from each child's legal guardian and from children older than 6 years, the ED nurse opens the next opaque randomization envelope to assign the participant to either the intervention or control group (Figure 1).

[figure not shown]

Figure 1. Randomized, controlled trial study flow chart regarding the clinical benefit of active testing.

Sample Collection and Pathogen Detection

After obtaining the written consent, fecal specimens will be collected by the nurses from the first stool after arriving in hospital. We collect fecal samples from all the children in both groups (n =

526) following the IVD (in vitro diagnostic) protocols. Also, all fecal samples will be processed according to IVD protocols to ensure reliability of the results. The pediatric nurses also collect rectal swab samples from all children. If vomiting occurs, vomit samples are also collected.

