Fecal specimens will be collected by the pediatric nurses from the first stool after arriving in the hospital. Sterile swab such as Copan Regular Flocked Swab 502CS01 will be used to insert the specimen into Cary-Blair medium (Copan FecalSwab) according to manufacturer's instructions. Rectal swab samples and vomit samples are collected using the same swab-kits. Swab is inserted approximately 2 cm into the rectum and rotated 3-4 times before removal. In case of vomiting, the swab is rotated in the gastric secretion. The specimens are then inserted into Cary-Blair medium solution, similarly to fecal samples.

Fecal samples will be tested with QIAstat-Dx gastrointestinal panel 2, which can detect 13 gastrointestinal bacterial species, 5 viral pathogens and 4 different parasitic species with results ready within 70 minutes (Table 1). Positive test result for *Clostridium Difficile* is complemented with an addendum "Clostridium Difficile is part of normal gut microbiota in children under 2 years of age". Following the IVD protocols, only fecal sample results are available to care taking physicians. Rectal swab and vomit results are only used for the methodological analysis (Figure 2). Threshold cycle (Ct) values for all samples will be recorded to estimate pathogen loads in different samples.

Study results are available to the clinicians mostly within a few hours from receiving the fecal sample in the intervention group. In the control group the results are delayed until 72 hours. By analyzing fecal samples in both groups, we ensure safety, transparency and enable a pathogen-specific impact analysis.

If the child is admitted to hospital and the test is considered necessary the following day, a new sample may be taken in addition to study samples.

Table 1. Pathogens detected by the QIAstat-Dx Gastrointestinal Panel 2

- Adenovirus F40/F41
- Astrovirus
- Norovirus (GI/GII)
- Rotavirus A
- Sapovirus (GI, GII, GIV, GV)
- *Campylobacter* (*C. jejuni*, *C. coli* and *C. upsaliensis*)
- *Clostridium difficile* (toxin A/B)
- Enterotoaggregative *Escherichia coli* (EAEC)
- Shigella/Enteroinvasive *Escherichia coli* (EIEC)
- Enteropathogenic *Escherichia coli* (EPEC)
- Enterotoxigenic *Escherichia coli* (ETEC) lt/st
- *Plesiomonas shigelloides*
- *Salmonella* spp.
- Shiga-like toxin-producing *Escherichia coli* (STEC) stx1/stx2* (including specific identification of *E. coli* O157 serogroup within STEC)
- *Vibrio vulnificus*
- *Vibrio parahaemolyticus*

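### The scoring rule for appropriate treatment makes no exception for C. difficile below age 2, which the protocol itself describes as normal flora, so one record can be scored either way on the primary outcome

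*Protocol*

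**What the plan says.** All the relevant text is in Protocol section 3.1.

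- **Primary outcome.** Three questions are answered for the first 72 hours, and a single YES makes the composite positive. Question 1 asks about correctly targeted antimicrobial treatment. The only criterion given for judging treatment is: "Antimicrobial treatment is considered appropriate if a bacterial pathogen has been found and the patient meets criteria for severe gastroenteritis". Severity is defined as "aged under 1 year or immunocompromised or hospitalized due to gastroenteritis".
- **Sample Collection and Pathogen Detection.** C. difficile (toxin A/B) appears under the heading "Table 1. Pathogens detected by the QIAstat-Dx Gastrointestinal Panel 2". The panel is one "which can detect 13 gastrointestinal bacterial species, 5 viral pathogens and 4 different parasitic species". A positive C. difficile result is reported with the addendum "Clostridium Difficile is part of normal gut microbiota in children under 2 years of age".
- **Timing of results.** Stool is tested in both arms: "We collect fecal samples from all the children in both groups". Intervention results mostly reach clinicians within a few hours. For controls, "In the control group the results are delayed until 72 hours". If a child is admitted and a test is thought necessary the next day, "a new sample may be taken in addition to study samples".
- **Secondary outcomes.** The proportion of correctly targeted antimicrobial treatment is also analysed on its own.

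**The concern.** The authors saw that a C. difficile detection in a very young child means something different and dealt with it in the laboratory report. They did not carry this into the outcome rule. The age band in which the protocol calls the organism normal (under 2) contains the whole band in which age alone counts as severe (under 1). For a treated infant with a C. difficile-only detection, both halves of the rule are therefore met automatically.

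Two careful assessors reviewing the same medical record could then place the child on opposite sides of the primary endpoint. Section 2 of the protocol hypothesises that testing will reduce inappropriate antibiotic use. Read literally, the rule could count as a success some treatment that the addendum suggests was not directed at a cause of illness.

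**Working it through.** **1. Is C. difficile inside the rule as written?** The bacterial entries in Table 1 are Campylobacter, C. difficile, EAEC, Shigella/EIEC, EPEC, ETEC, Plesiomonas, Salmonella, STEC, three Vibrio species and Yersinia. That makes 13, the number stated in the text, and 12 without C. difficile. The protocol therefore counts it among the panel's bacteria and lists it under a heading that calls the targets pathogens. The outcome rule removes nothing from that list.

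**2. Which records are affected?** Treated children whose only bacterial detection is C. difficile and who are either under 1 year, or aged 1 to under 2 and hospitalized for gastroenteritis. The immunocompromised limb adds little, because severe immunosuppression is an exclusion criterion.

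| | Rule as written | Addendum followed |
|---|---|---|
| Question 1 (correctly targeted) | YES | NO |
| Question 2 (untargeted avoided) | not needed | NO |
| Composite | positive | negative, unless question 3 is YES |

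If question 3 is YES anyway, the composite is unchanged and only the secondary proportion moves. Untreated children are not affected, since question 1 cannot be YES for them.

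**3. The plan's own figure.** For 20% versus 10%, two-sided 5% (sidedness is not stated, so this is assumed) and 80% power, the usual formula gives 199 per arm, or 219 with continuity correction. 219 × 1.2 = 262.8, rounded up to the stated 263. Losing 20% of 263 leaves 263 × 0.80 = 210 evaluable per arm. The scoring question does not change the sample size.

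**4. Effect per misscored child.** 1/210 = 0.48 percentage points. The planned 10-point difference is 0.10 × 210 = 21 children.

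Take a true composite rate of 10% in both arms (the protocol's control rate), 210 per arm and a pooled z-test at two-sided 5%. Treat each misscored child as a shift of 1/210 in that arm's rate, with questions 2 and 3 NO. Exact enumeration of the two binomials gives:

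| Misscored, intervention / control | P(significant for intervention) |
|---|---|
| 0 / 0 | 0.0245 |
| 1 / 0 | 0.0353 |
| 2 / 0 | 0.0494 |
| 2 / 1 | 0.0352 |
| 1 / 1 | 0.0246 |
| 5 / 5 | 0.0248 |

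The counts are illustrations, not estimates. By symmetry, error confined to the control arm gives the same figures in favour of control.

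**5. Direction.** Net shift = q × (aI − aC), where q is the share of children who meet the severity rule with a C. difficile-only detection under age 2, and aI and aC are their treatment rates by arm. The protocol gives none of the three, so the ranges below are assumptions.

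- *Found* means known to clinicians within 72 hours. Control results are withheld for that whole window, so apart from a repeat sample the control error is about 0. With q from 2% to 15% and aI from 5% to 30%, the shift runs from 0.02 × 0.05 = 0.1 to 0.15 × 0.30 = 4.5 points in favour of the intervention.
- *Found* means any study stool result in either arm. With q from 5% to 15% and rates from 5% to 30%, the shift runs from 0.15 × (0.05 − 0.30) = −3.75 to +3.75 points, and is zero when the treatment rates are equal.

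**The case against.** **Normal flora is not a pathogen.** The rule requires a pathogen, and the addendum says what the organism is at this age, so an assessor may naturally leave it out. The Table 1 heading describes a commercial panel and is not an outcome definition. This is a fair reading, but no sentence in the protocol adopts it, and the literal reading is equally available. The point is that the text supports both.

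**Appropriate is not the same word as correctly targeted.** Equating them is an inference. *Targeted* could mean directed at the organism found, in which case empirical treatment of a child who happens to carry C. difficile would not score. That stands as a caveat. The protocol offers no other definition of correctly targeted, however, and the gap between the terms is a further reason to fix the wording.

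**A statistical analysis plan or scoring guide may settle it.** It may. But the protocol does not leave the definition open; it states a rule that conflicts with its own text a few paragraphs earlier.

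**The effect is small.** An affected child must be under 2, meet the severity rule, have no other bacterial detection, be treated within 72 hours and have no other YES. The addendum may itself make such treatment rare. The probabilities in the table apply to any misscored child from any cause and say nothing about how often C. difficile produces one. All of this stands.

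**The direction.** A reader might infer that the error favours the intervention arm, because only there can a study result prompt treatment inside the window. The documents do not establish this. If stool results from both arms are used for scoring, an empirically treated control child with a positive sample earns the same credit. The addendum, which in practice reaches only intervention clinicians in time, could also lower treatment in that arm, so the sign can reverse.

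**Conclusion.** The concern holds as a conflict between a stated scoring rule and the protocol's own description of C. difficile under age 2. It reaches the primary composite through question 1 and the secondary proportion of correctly targeted treatment directly. It rests on taking appropriate as the definition of correctly targeted.

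The size is unknown and may be near zero, because the protocol gives no C. difficile prevalence, age mix or treatment rate. What can be said is 0.48 points per net child against a planned difference of 21 children. The direction is conditional on the meaning of *found*: almost wholly towards the intervention arm if it means known within 72 hours, and zero or either way if any study stool result counts. No claim of bias for one arm should be made beyond that.

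A lesser wording mismatch sits in the same rule. The questions speak of antimicrobials and the panel reports four parasites, but the criterion says bacterial and the sample-size text says antibiotic. A reader might infer that treating a parasite could never be scored appropriate; that goes too far, since the rule says *if* and not *only if*.

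**What to change.** Before outcomes are scored, reconcile the addendum and the Primary outcome rule in the scoring definition:

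1. State that, for scoring only, a C. difficile-only detection at an age where the protocol calls the organism normal flora does not by itself count as a bacterial pathogen having been found.
2. State whether *found* refers to results known to clinicians within 72 hours or to any study stool result.
3. Use one term in question 1 and in the criterion.
4. Apply the rule identically in both arms.
5. Report by arm how many children change score under item 1, so that the size becomes known.

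This concerns how records are classified and implies nothing about who should be treated. In the same edit, align bacterial and antibiotic with antimicrobial.

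The cost is one or two sentences and a small extra table. Panel results come from the study's own stool tests in both arms and treatment from the planned record review, so no new data should be needed and the sample size is unchanged.

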Secondary outcomes are proportion of correctly targeted antimicrobial treatment, proportion of conditions in need for hospitalization or specific follow-up, time needed for clinician to receive the results of the samples, length of hospital stay, time to correct diagnosis, resolution of symptoms, laboratory and radiology costs, total costs, need for surgical consultation and proportion of patients needing surgical procedure, proportion of unscheduled revisits, proportion of correctly isolated patients or correct use of personal protective equipment and the number of consultations for pediatric infectious diseases specialist.

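### The single stated test of appropriate antimicrobial treatment fits neither the symptom-based population nor a panel that reports parasites, so some treatment is likely to be misclassified in the primary outcome

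*Protocol*

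**What the plan says.** All references are to the protocol, section 3.1, unless noted.

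- **Primary outcome.** Question 1 is "Was correctly targeted antimicrobial treatment started" and question 2 is "Was untargeted antimicrobial treatment avoided". Question 3 asks about planned follow-up for risk of complications. The combining rule is "When any of these questions is answered YES, the composite variable is considered positive". The window is 72 hours from first contact.
- **The test.** One criterion follows: "Antimicrobial treatment is considered appropriate if a bacterial pathogen has been found and the patient meets criteria for severe gastroenteritis". Severity is met by a child "aged under 1 year or immunocompromised or hospitalized due to gastroenteritis". The term *untargeted* has no definition of its own, and no exception or adjudication step is given.
- **Population.** Any one of the listed symptoms is enough for eligibility, and the list includes "abdominal pain and/or watery stool" as well as vomiting. Neither a surgical abdomen nor a non-gut infection is an exclusion.
- **Secondary outcomes.** These include "need for surgical consultation and proportion of patients needing surgical procedure". The Abstract also lists the proportion of untargeted treatment.
- **Panel.** Besides 13 bacterial targets it covers "5 viral pathogens and 4 different parasitic species". Clinicians in the intervention arm mostly see results within hours; in the control arm they are held back for 72 hours.

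**The concern.** The test is written for bacterial gastroenteritis, but it is the only key to two of the three questions in the primary outcome, for a wider population and a wider panel. Two groups are affected.

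(a) Children treated for something other than gastroenteritis. A 7-year-old given an antibiotic around an operation for appendicitis is not in hospital because of gastroenteritis, so the treatment fails the test. A gut panel has little bearing on that decision, yet it enters the outcome as untargeted use.

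(b) Children treated because the panel found a parasite. The questions speak of antimicrobials, but the test accepts only a bacterium. Acting on the panel's own result is then scored as untargeted, mostly in the arm that sees the result inside the outcome window.

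At stake is whether questions 1 and 2, and the secondary outcome on untargeted treatment, measure what section 2 sets out to measure: appropriate and inappropriate antibiotic use.

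**Working it through.** **1. The plan's own figure.** Inputs: 20% against 10%, α 5% (taken as two-sided), power 80%, 1:1, 20% loss. The pooled formula gives [1.96·√(2·0.15·0.85) + 0.8416·√(0.2·0.8 + 0.1·0.9)]² / 0.10² = 199 per arm. The continuity correction raises this to 219, and 219 × 1.2 = 262.8, or 263 per arm as stated. The present point does not depend on this figure. After 20% loss, 263 × 0.8 ≈ 210 per arm remain.

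**2. Applying the test case by case.** Assume that treatment failing the test is untargeted, and that a child given no antimicrobial has avoided untargeted treatment.

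| Child | Question 1 | Question 2 |
|---|---|---|
| Age 7, antibiotic for appendicitis, either arm | NO | NO |
| Age 3, vomiting, antibiotic for a proven urinary infection, either arm | NO | NO |
| Under 1 year, antibiotic for a proven non-gut bacterial infection, either arm | can be YES | can be YES |
| Intervention arm, parasite reported, treated for it, no bacterium found | NO | NO |
| Control arm, same parasite, result not yet seen, untreated | NO | YES |

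The third row arises because the test does not say the bacterium must come from stool, and age under 1 year alone meets the severity condition. The last two rows differ in the direction that harms the intervention arm. In every row question 3 can still make the composite positive.

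**3. Size of group (a).** The protocol does not give the share *f* treated for a non-gut or surgical condition; 5%, 10% and 15% are assumptions. The counts are upper limits, because some infants qualify.

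- Of 263 per arm: 263 × 0.05, 0.10, 0.15 ≈ 13, 26, 39 children.
- Of the 210.4 expected after loss: about 11, 21, 32.

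Suppose the panel lowers unnecessary antimicrobials for gastroenteritis from 5% to 2.5% (assumption). The scored rates are 5 + *f* and 2.5 + *f*.

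| *f* | Scored untargeted, control vs intervention | Absolute difference | Relative reduction, 2.5/(5 + *f*) |
|---|---|---|---|
| 0% | 5.0% vs 2.5% | 2.5 points | 50% |
| 5% | 10.0% vs 7.5% | 2.5 points | 25% |
| 10% | 15.0% vs 12.5% | 2.5 points | 16.7% |
| 15% | 20.0% vs 17.5% | 2.5 points | 12.5% |

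**4. Size of group (b).** Parasites are 4 of 22 targets (13 + 5 + 4 = 22). That is a count of targets, not a frequency of detection or treatment, so no estimate is possible.

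**5. Effect of rescoring on power.** If a share *m* of children in both arms moves from NO to YES and the 10-point difference is kept, power at 210 per arm (two-sided 5%, no continuity correction) is:

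| *m* (assumed) | Rates | Power |
|---|---|---|
| 0% | 20% vs 10% | 82% |
| 2% | 22% vs 12% | 78% |
| 5% | 25% vs 15% | 73% |
| 10% | 30% vs 20% | 66% |

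**The case against.** The best defence is that the scoring is inferred. The criterion says *if*, not *only if*, and nowhere states that treatment failing it is untargeted. Being framed around gastroenteritis severity, it could be read as covering only antimicrobials given for gastroenteritis, and a SAP or review manual may say so. This stands as a limit on certainty. It does not remove the point: section 2 states the aim in terms of appropriate and inappropriate antibiotics, and the protocol offers no other rule. Record reviewers must apply this one or improvise.

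A second defence is that the bacterial limit is deliberate, since the Abstract, section 2 and the sample size text speak of bacteria or antibiotics. That is plausible, but questions 1 and 2 say antimicrobial, so the wording still needs reconciling.

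Third, the low planning rates of 20% and 10% may mean that the sponsor does not score every untreated child YES on question 2. If so, the contrast in the last two rows of the case table weakens.

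A reader might go further and infer any of the following, which the documents do not support:

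- *Every antimicrobial for a non-gut infection fails.* Infants can literally qualify.
- *The primary comparison loses half or more of its effect.* The relative figures concern untargeted treatment alone and rest on assumed inputs. The absolute difference is unchanged, the sample size is planned on absolute proportions, and question 3 stays open.
- *Group (a) biases the comparison.* Randomisation should balance it.
- *Group (b) arises almost only in the intervention arm, or is material.* Admitted children may have a new sample the next day, and no parasite frequency is given.

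**Conclusion.** The point holds as a mismatch between a stated scoring rule and the population and panel to which it applies. It rests on the natural, but not explicit, reading that treatment failing the test is untargeted.

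On that reading, group (a) mainly adds misclassification: the relative reduction in untargeted treatment shrinks (from 50% to between 25% and 12.5% under the assumed inputs) and the absolute difference stays at 2.5 points. Group (b) can bias against the intervention arm. Its size cannot be derived from the protocol and may be small; it also assumes that an untreated child scores YES on question 2.

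The rule should be clarified before outcomes are scored, because it defines the primary outcome and the correction is cheap. The evidence does not show that the trial's main comparison is invalid as it stands.

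**What to change.** Amend the Primary outcome text in section 3.1. The change is to scoring only and alters no child's treatment.

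1. State that questions 1 and 2 apply to antimicrobials given for gastroenteritis, and define *untargeted* explicitly.
2. Record the documented indication in the medical record review already planned, judged blind to arm. Report antimicrobials for non-gastrointestinal or surgical indications separately, not as untargeted, and state what value question 2 takes for a child whose only antimicrobial was of that kind.
3. Reconcile *antimicrobial* with *bacterial pathogen*. The sponsor should list which panel organisms, parasites included, count as a target, and say for each whether the severity condition applies. Adding parasites to the wording alone would leave that condition in force, so a child over 1 year who is neither immunocompromised nor in hospital would still fail.
4. Check the planning rates of 20% and 10% against the revised definition.

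The cost is a short amendment and one extra field in the record review, plus a judgement of indication by the reviewer. Moving non-gut cases from NO to YES in both arms does not raise power and may lower it, as the last table in the working shows; the gain is a more valid measurement, not efficiency.
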